9.6. Patient exit

Patients may be exited from the study under the following circumstances:

- Included in the trial in violation of the inclusion and/or exclusion criteria
- Patient chooses to withdraw
- Patient death before transoesophageal echocardiography

9.7. Constraints related to the research

The person can participate in another interventional study if the related intervention starts after the transoesophageal echocardiography. There is no exclusion period during which the participant cannot participate in another study after completing this one.

9.8. Blood sample collection

Peripheral blood sample is collected for d-dimer assay at the inclusion.

The following requirements will be followed for the collection:

- Blood samples will be collected in 0.109M (i.e., 3.2%) trisodium citrate anticoagulant, 1 volume of citrate for 9 volumes of blood, in accordance with CLSI Guideline H21-A5 Collection, Transport, and Processing of Blood Specimens for Testing Plasma-Coagulation Assays and Molecular Haemostasis Assays (Vol.28; No.5)(24). Two will be collected to allow sufficient plasma volume for the study.

- Blood samples will be centrifuged within 4 hours after blood draw at 2,000-2,500g for 15 minutes at a temperature close to 18°C, and then plasma samples will be divided in at least 4 aliquots of 0.6 ml each.
- Each aliquot will be de-identified (i.e., only an anonymous number will be available in the data collection form in order to ensure patient anonymity).
- One aliquot will be tested fresh (within 6 hours after blood collection).
- The remaining plasma samples will be frozen and stored at -70°C or colder (as soon as possible and no more than 2 hours after plasma collection).

Frozen samples will be used to constitute a plasma bank. It will be used to confirm results with the STA-Liatest DDi Plus and to assess other d-dimer assays with kits currently under development. Samples will be kept for 10 years. After which, the samples will be destroyed by incineration. Under no circumstances will these samples be used in other studies.

10. Study follow-up

10.1. Protocol deviations

A deviation is defined as an event where the exact instructions written in this protocol, the clinical trial agreement or the applicable regulations have not been followed. Deviations are classified by occurrence, i.e., sporadic vs. repeated and seriousness, i.e., major vs. minor.

Major deviations may impact subject safety, alter the risk/benefit ratio, compromise the integrity of the study data, and/or affect subjects' willingness to participate in the study. Minor deviations do not impact subject safety, compromise the integrity of the study data, or affect subjects' willingness to participate in the study.

Investigators are required to obtain prior approval from the sponsor before initiating deviations from the protocol, except where necessary to protect the life or physical well-being of a subject in an emergency. Such approval will be documented in writing and maintained in study files. Prior approval is generally not expected in situations where unforeseen circumstances are beyond the investigator's control; however, the event is still considered a deviation and must be recorded in the subject Case Report Form.

Protocol deviations will be reported to the sponsor using suitable forms, regardless of whether medically justifiable, pre-approved by the sponsor or taken to protect the subject in an emergency.

Investigators must also adhere to procedures for reporting study deviations to IRB/EC in accordance with their specific IRB/EC reporting policies and procedures.

The monitor will discuss deviations with relevant site personnel, and will document them on monitoring visit reports. If needed, a Note to File will be issued and filed in the relevant file and a copy sent to the sponsor.

The sponsor will review records of deviations and will consider the need for corrective and preventive action and further external reporting to regulatory authorities. A summary report classifying and summarizing the deviations per type will be issued and reviewed by the sponsor personnel.

Deviations will be summarized and included in the study report. Assessment and discussion of their potential impact / lack of impact on study results will be addressed.

10.2. Adverse event reporting

10.2.1. Definition

Adverse Device Effect (ADE): adverse event related to the use of a medical device.

Note 1: This definition includes any adverse event resulting from insufficient or inadequate instructions for use or the deployment, implantation, installation, or operation, or any malfunction of the medical device.

Note 2: This definition includes any event resulting from user error or from intentional misuse of the medical device

Adverse Event (AE): Any untoward medical occurrence, unintended disease or injury, or untoward clinical signs (including abnormal laboratory findings) in subjects, users or other person, whether or not related to the medical device

Note 1: This definition includes events related to the medical device or the comparator

Note 2: This definition includes events related to the procedure involved

Note 3: For users or other persons, this definition is restricted to the medical device.

Serious Adverse Event (SAE): An Adverse Event that:

- a) Led to death,
- b) Led to serious deterioration in health of the subject, that either resulted in
 - life-threatening illness or injury
 - permanent physical impairment
 - in-patient hospitalization or prolongation of existing hospitalization
 - medical or surgical intervention to prevent permanent physical impairment
- c) Led to foetal distress, foetal death or congenital abnormality or birth defect.

Note: Planned hospitalization for a pre-existing condition without serious deterioration in health is not considered as a serious event.

Serious Adverse Device Effect (SADE) (ISO14155-2011): Adverse device effect that has resulted in any of the consequences of a serious adverse event.

Procedure-Related Adverse Event: An event that occurs due to the procedure and cannot be directly attributed to a particular device or implant tool.

Unanticipated Serious Adverse Device Effect: serious adverse device effect which by its nature, incidence, severity or outcome has not been identified in the current version of the risk analysis report.

10.2.2. Description of expected SAE

SAE related to atrial rhythm disorder:

- Congestive Heart Failure
- Cardiogenic shock
- Intra-atrial thrombus
- Cardioembolic stroke
- Myocardial infarction and unstable angina for patients with ischemic disease

SAE related to medical treatment:

- Hemorrhage
- Ventricular rhythm disorder
- Bleeding or pain at the femoral puncture point
- Bradycardia
- Anticoagulant overdose

10.2.3. Event review and reporting

10.2.3.1. Event review

Upon the signature of the consent, the investigator is responsible for the collection of all adverse events. He reports all serious and non-serious adverse events (biological and clinical) that occur between the signature of the consent and the end of patient participation.

10.2.3.2. Reporting

Adverse reactions/adverse reactions/incidents should be reported in accordance with local requirements.

10.2.4. Information for data collection

All information required by the protocol must be recorded on the case report forms and an explanation must be provided for each missing data. The data must be collected as it is obtained and transcribed in these case report forms clearly and legibly.

Data will be collected through electronic case report forms.

10.2.5. Quality control

A clinical researcher mandated by the sponsor visits each research centre on a regular basis, when the research is set up, once or several times during the course of research,

according to the rhythm of the inclusions and at the end of the research. During these visits and in accordance with the risk-based monitoring plan (participant, logistics, impact, resources), the following elements will be reviewed:

- informed consent,
- compliance with the research protocol and the procedures defined therein,
- quality of the data collected in the CRF: accuracy, missing data, consistency of data with source documents (medical records, appointment books, originals of laboratory results, etc.)

A monitoring report will be written after each visit.

Visits will be on-site or through teleconferences or webconferences.

10.2.1. Audit and inspection

The centre can be audited at any time by persons appointed by the sponsor and independent of the persons conducting the research. Its objective is to verify the safety of the participants and the respect of their rights, the respect of the applicable regulations and the reliability of the data.

An inspection may also be carried out by a competent authority (ANSM for France or EMA in the context of a European trial).

The audit, as well as the inspection, can happen at all research stages, from the development of the protocol to the publication of the results and the classification of the data used or produced during the research.

The investigators agree to comply with the sponsor requirements for an audit and the competent authority for a research inspection.

11. Study conclusion and statistical consideration

11.1. Sample size rationale

Given the low rate of atrial thrombi (about 2 % of patients eligible to atrial fibrillation ablation), this study requires a high number of participants in order to allow reliable estimation of diagnostic performance.

To detect a 0.5 % deviation between two negative predictive values (binomial test), 2,000 patients are required for a power of 70 %; 2,400 patients for a power of 80 %; and 3,000 patients for a power of 90%.

Due to the high enrolment capacities of this multicentre study and its simplicity for the centres involved, it was chosen to focus on the power of the study and to retain a sample size of 3,000 patients.

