3.1.2. Description of the ATE score to be validated

A preliminary study, EXTRALUCID-d (NCT02199080), included 2,494 patients hospitalized for an atrial fibrillation ablation. It studied a combined clinical-biological score, the Atrial Thrombus Exclusion (ATE), associating thromboembolic risk factors (hypertension, cardiac insufficiency, history of stroke) and d-dimer level for the prediction of intra-atrial thrombus.

The primary outcome was the number of intra-atrial thrombus diagnosed by transoesophageal echocardiography. A zero ATE score, defined by no cardiac insufficiency, no hypertension, no history of stroke, and D-dimer < 270 ng/mL, had a negative predictive value of 100% for the diagnosis of intra-atrial thrombus.

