3.3. Overall risk/benefit assessment

We believe that the benefit / risk balance is very favourable, given that the risk of the study is negligible. The confirmation of an excellent negative predictive value of the ATE score would prevent one transoesophageal echocardiography out of three during the period of preoperative endocardial ablation of atrial fibrillation.

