7.2. Feasibility and recruitment modalities

The investigating centres have the following characteristics:

- The number of ablation of atrial fibrillation is greater than 50 per year,
- Transoesophageal echocardiography is performed routinely before any ablation of atrial fibrillation.

Investigating centres compliance with those characteristics will be documented upon selection.

In each centre, patient eligible for atrial fibrillation or left flutter ablation will be screened. In agreement with the physician performing the procedure, the study will be explained and proposed to the eligible patients by an investigator at the admission or at the pre-ablation consultation. It is strongly recommended to include patients consecutively in order to limit

selection bias. We plan to open circa 25 centres in France and Europe, with an average of 120 patients per centre. The provisional duration of enrolment is 30 months.

8. Material and Methods

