11.2. Statistical analysis plan

The analysis will be performed at the end of the trial. There is no interim analysis planned.

The index test is the ATE score. A zero score is a negative result, while a score above zero is a positive result.

The reference test is the transoesophageal echocardiography. The negative condition is the absence of thrombus, and the positive condition is the presence of thrombus.

Demographics, medical history, clinical characteristics and diagnosis will be presented in tables with descriptive statistics for each sub-population (positive and negative condition) and for the entire analysed population, as follows:

- For quantitative variables: mean and standard deviation,
- For qualitative variables: count, percentage (excluding missing denominator data) and 95% confidence intervals.

ATE score sensitivity, specificity, positive predictive value, negative predictive value, and 95% confidence intervals will be calculated.

Primary objective will be met, if these parameters are similar with the ones obtained during the first study.

The ATE score will be considered clinically relevant if a negative predictive value of 100 % is obtained for a zero score.

12. Ethical and legal aspects

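### Are the 70/80/90% power figures in section 11.1 wrong because they ignore that only zero-score patients enter the negative predictive value?

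*Combined protocol and SAP*

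**What the plan says.** Section 11.1 states: "To detect a 0.5 % deviation between two negative predictive values (binomial test), 2,000 patients are required for a power of 70"%, then "2,400 patients for a power of 80 %; and 3,000 patients for a power of 90"%. It retains 3,000 in order to favour power, citing the centres' high enrolment capacity and the study's simplicity. It names a binomial test but gives no reference or alternative NPV, alpha, number of sides, or one- or two-sample form.

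Four other places bear on the point:

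- Section 11.2 defines the index test: "A zero score is a negative result, while a score above zero is a positive result". The NPV is therefore estimated in zero-score patients only. The same section plans 95% confidence intervals for all the accuracy measures.
- Section 3.1.2 gives the only NPV in the documents: in the first study a zero score "had a negative predictive value of 100% for the diagnosis of intra-atrial thrombus".
- Section 3.3 says that confirming the score "would prevent one transoesophageal echocardiography out of three". This is the nearest the documents come to a zero-score share.
- Section 7.2 covers feasibility: "We plan to open circa 25 centres in France and Europe, with an average of 120 patients per centre".

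**The concern.** The sentence in section 11.1 counts patients, but an NPV has only test-negative patients in its denominator. If one third of those enrolled score zero, the 3,000 become about 1,000, and a calculation made on 3,000 would overstate the power for the NPV. The obvious check adds to the suspicion: the documented 100% against 99.5%, at the conventional 5% level, does not give 70/80/90% in the usual one- and two-sample forms.

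The study may lead to transoesophageal echocardiography being omitted when the score is zero. A reader would want to know what shortfall in NPV the zero-score group can reveal. If the stated power were wrong, the main justification for 3,000 patients would fall.

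**Working it through.** **Inputs.** From the documents: N = 2,000/2,400/3,000 with power 70/80/90% and a difference of 0.005 (section 11.1); NPV 100% (section 3.1.2). Assumed: alpha and number of sides; alternative NPV 99.5%; zero-score share one third (from section 3.3), giving 667/800/1,000, with a range of one quarter to one half at N = 3,000 (750 to 1,500).

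**Step 1. Documented NPV at 5%.** The two-group results use the pooled normal approximation.

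| Form, 100% vs 99.5% | N = 2,000 | 2,400 | 3,000 |
|---|---|---|---|
| One-sample, 1 − 0.995^n, n = N/3 | 96.5% | 98.2% | 99.3% |
| One-sample, n = N | >99.99% | >99.99% | >99.99% |
| Two groups of N, two-sided | 88.6% | 93.5% | 97.3% |
| Two groups of N/2, one-sided | 72.4% | 79.1% | 86.4% |
| Two groups of N/2, two-sided | 61.0% | 68.9% | 78.3% |
| Two groups of N/3, two-sided | 44.7% | 51.7% | 61.0% |

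In the one-sample form any thrombus contradicts 100%, so alpha plays no part. No row gives 70/80/90%; the nearest is 3.6 points off.

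**Step 2. The same pair at two-sided 1%.** Section 11.1 does not fix alpha at 5%. For two equal groups,

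n per group = [z(1−α/2)·√(2·p̄·(1−p̄)) + z(power)·√(p1(1−p1) + p2(1−p2))]² / δ²

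With p1 = 1, p2 = 0.995, p̄ = 0.9975 and δ = 0.005, the two roots are √0.0049875 = 0.070622 and √0.004975 = 0.070534. With z(0.995) = 2.5758, the first term is 0.18191.

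- 70%: (0.18191 + 0.5244 × 0.070534)² / 0.000025 = 1,917
- 80%: (0.18191 + 0.8416 × 0.070534)² / 0.000025 = 2,329
- 90%: (0.18191 + 1.2816 × 0.070534)² / 0.000025 = 2,966

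Rounded up to the next hundred, these are 2,000, 2,400 and 3,000. Solved the other way, power at the stated sizes is 72.3/81.4/90.4%.

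**Step 3. Other choices that also fit.** With a one-sample exact test at two-sided 5%:

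- 99.05% vs 99.55% on all N gives 70.6/80.0/90.9%;
- 99.96% vs 99.46% on one third of N gives 69.8/80.6/90.6%.

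The first uses all enrolled patients and the second only the assumed zero-score third. The stated figures therefore cannot identify the denominator.

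**Step 4. What the trial delivers in zero-score patients.**

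| Zero-score patients out of 3,000 | Chance of ≥1 thrombus if true NPV is 99.5% | Two-sided 95% lower limit if none seen, 0.025^(1/n) |
|---|---|---|
| 750 | 97.7% | 99.51% |
| 1,000 | 99.3% | 99.63% |
| 1,500 | 99.9% | 99.75% |

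Across the whole range, a clean result puts the lower limit above 99.5%, so it would exclude a shortfall of 0.5 points.

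**The case for a change.** The strongest case for a change is that power is the stated reason for 3,000, and nobody can check it from the document. The fit in step 2 does not clear this up. An alpha of 1% appears nowhere in the documents, and the only level mentioned is the 95% of the confidence intervals. The normal approximation is poor this close to 100%: the actual power of that pooled test is about 87/95/99%. The fit also takes N enrolled patients as the group size, so it leaves the denominator question open. If the 99.05% vs 99.55% calculation on all N was the one used, power on one third of N would be only 19.8/30.2/34.2%.

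What stands is that the inputs and the conversion to zero-score patients are not written down, and that the stated power may not apply to the zero-score group. What does not stand is the step from there to an error. Step 2 is not offered as what the sponsor did. It shows that failure to reproduce the figures from the documented NPV depends on assuming 5%. The 100% is itself an assumed planning value, since section 11.1 does not say that it is one of the two NPVs compared.

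**Conclusion.** The concern does not call for a change. Section 11.1 is incompletely reported, but its figures are not shown to be wrong. They fit several undocumented sets of inputs, including one that uses the documented 100%, and the fits point to different denominators.

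Nothing in the conduct or analysis turns on the answer. Section 11.1 takes the largest of its three sizes, and it equals what section 7.2 expects to recruit (25 × 120 = 3,000). No rule in section 11.2 uses the planned power. The analyst will compute the NPV in zero-score patients, because section 11.2 defines it so, and will report it with a 95% confidence interval. That interval uses the actual zero-score count and will tell the reader more than a restated planning power.

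The size of the study is adequate on the figures available: with about 1,000 zero-score patients, a true NPV of 99.5% would show at least one thrombus with 99.3% probability, and none observed would give a lower limit of 99.63%. This rests on the one-third share read from section 3.3; at 750 to 1,500 zero-score patients the figures are 97.7% to 99.9% and 99.51% to 99.75%. Listing the inputs would be tidier, but would alter neither enrolment nor any result.

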11.2. Statistical analysis plan

The analysis will be performed at the end of the trial. There is no interim analysis planned.

The index test is the ATE score. A zero score is a negative result, while a score above zero is a positive result.

The reference test is the transoesophageal echocardiography. The negative condition is the absence of thrombus, and the positive condition is the presence of thrombus.

Demographics, medical history, clinical characteristics and diagnosis will be presented in tables with descriptive statistics for each sub-population (positive and negative condition) and for the entire analysed population, as follows:

- For quantitative variables: mean and standard deviation,
- For qualitative variables: count, percentage (excluding missing denominator data) and 95% confidence intervals.

ATE score sensitivity, specificity, positive predictive value, negative predictive value, and 95% confidence intervals will be calculated.

Primary objective will be met, if these parameters are similar with the ones obtained during the first study.

The ATE score will be considered clinically relevant if a negative predictive value of 100 % is obtained for a zero score.

12. Ethical and legal aspects

12.1. Access right to files and source data

12.1.1. Data access

Acceptance of participation in the protocol implies that the investigators will make available the individual documents and data strictly necessary for monitoring, quality control and audit to those who have access to these documents in accordance with the laws and regulations in force.

12.1.2. Source data

Source data are all information in original documents or in authenticated copies of these documents relating to clinical examinations, observations or other research activities necessary for the evaluation of the research. The documents in which the source data are stored are called the source documents.

12.1.3. Data confidentiality

In accordance with current legislation, those with direct access to the source data will take all necessary precautions to ensure the confidentiality of information about experimental data, and participating patients and, in particular, their identity and the results obtained. These persons, in the same way as the investigators themselves, are subject to professional secrecy.

During and after the research, the data collected from the patients and forwarded to the sponsor by the investigators (or other specialists) will be made anonymous. They must in no case show clearly the names of the concerned persons or their address.

The sponsor will ensure that each participating patient to the research has given his consent for access to his individual data.

12.2. Ethical conduct of the study

The sponsor and the investigators ensure that this research is carried out in accordance with Law No. 2012-300 of March 5th 2012 on research involving the human person and in agreement with good clinical practice (ICH version 4 of November 9th 2016 and Decision of November 24th 2006) and the Helsinki Declaration (which can be found in its full version at <http://www.wma.net>).

The research shall be conducted in accordance with this Protocol. Except in emergency situations requiring specific therapeutic procedures, the investigators undertake to comply with the protocol in all respects.

This research has been approved by a French Committee for the Protection of persons and other local ethics committees for sites selected out of France.

The data recorded are subject to a computerized treatment in compliance with the law n°78-17 of January 6th 1978 relating to data processing, files and freedoms as amended by Law 2004-801 of August 6th 2004.

This research falls within the framework of the "Reference Methodology" (MR-001) in application of the article 54 paragraph 5 of the amended law of January 6th 1978 relating to information, files and freedoms. This change was approved by decision of January 5th 2006, updated on July 21st 2016. The Groupe Hospitalier de la Rochelle Ré Aunis has signed a commitment to conform to this "Reference Methodology".

